4.3.2. Procedures for withdrawal or discontinuation

The efficacy and safety examinations to be completed upon trial withdrawal as specified in the protocol must be completed as much as possible. In addition, the safety follow-up should be completed along with fully documented AEs and their outcomes. The investigator can recommend or provide new or alternative treatments to the subject based on the condition of the subject. Patients showing no progressive disease need to be continuously followed-up for imaging evaluation until the subjects begin a new anti-tumor treatment or show progressive disease.

Survival status should still be followed even if the subject refuses to visit the study site, unless the subject withdraws consent to provide further information or consent to be further contacted. In such case, no study assessment is performed, nor any data are collected. The sponsor can retain and continue to use all data collected before withdrawal of informed consent, unless the subject requests a retraction of collected data.

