5.3. Dose Modifications

The dose of the investigational drugs may be modified according to the toxic side effects of the investigational drugs. The options of dose modification include: dose interruption, dose reduction, change in route of administration, and discontinuation.

In this study, SHR-1210 treatment may be interrupted for up to 12 weeks;

In addition to treatment interruption, the dosage of SHR-1210 can be reduced to 3 mg/kg, q2w, for subjects with a body weight of less than 50 kg during the treatment.

Dose modifications caused by apatinib-related toxicity include: dose interruption, modification of method of administration (first modification: 5 days of drug administration followed by 2 days of dose interruption; re-modification: 7 day of drug administration followed by 7 day of dose interruption), and dose termination. A changed route of administration for apatinib shall never be resumed for the subject.

If apatinib-related AE occurs during the study, such as hypertension, proteinuria, or hand-and-foot syndrome, apatinib may be interrupted, and can be resumed, administered in a modified route, or discontinued accordingly when the toxicity resolves. Subjects may continue SHR-1210 as monotherapy if apatinib treatment is discontinued.

For immune-related toxicity occurring during the trial, such as immune-related pneumonia, hepatitis and colitis, the dosing of SHR-1210 and apatinib should be interrupted as appropriate. The dosing can be resumed when the toxicity returns to Grade ≤ 1 or baseline levels (for subjects with abnormal laboratory measurements such as ALT/AST and TBIL at baseline). The dosing of SHR-1210 should be resumed first. The dosing of apatinib can be resumed when no significant abnormality is observed within 7 to 14 days after SHR-1210 administration. The route of subsequent administration of apatinib should be modified.

During the study, in case of \geq Grade 3 immune-related pneumonia, \geq Grade 3 elevation in TBIL (recurrent), Grade 4 elevation in ALT/AST (recurrent), other Grade 4 immune-related toxicities (except for hypothyroidism), Grade 4 injection reactions, or the interruption of SHR-1210 administration for more than 12 weeks due to immune-related toxicity but the toxicity can still not return to \leq Grade 1 or baseline levels (subjects with baseline abnormality), the administration of SHR-1210 should be terminated permanently.

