Proteinuria (without significant increase in blood creatinine)	Grade 3 (24 h protein urine quantification)	No	Yes	Toxicity returns to Grade ≤ 2	Treat with apatinib for 5 days and hold for 2 days; Second onset of Grade 3 proteinuria: treat with apatinib for 7 days and hold for 7 days;	Discontinue apatinib treatment if Grade 3 proteinuria recurs after 2 modifications
Hand-and-foot syndrome	Grade 3	No	Yes	Toxicity returns to Grade ≤ 1	Treat with apatinib for 5 days and hold for 2 days; Second onset of Grade 3 hand-and-foot syndrome: treat with apatinib for 7 days and hold for 7 days;	Discontinue apatinib treatment if Grade 3 hand-and-foot syndrome recurs after 2 modifications
Headache	Grade 2 headache lasting ≥ 7 d despite symptomatic treatment, or Grade 3 headache	No	Yes	Toxicity returns to Grade ≤ 1	Treat with apatinib for 5 days and hold for 2 days; Second onset: treat with apatinib for 7 days and hold for 7 days;	Discontinue apatinib treatment if the event recurs after 2 modifications

The investigator may consider suspend the treatment for subjects who experience persistent and significant toxicities despite symptomatic treatment, including persistent Grade 2 or higher non-hematologic toxicities (except for asymptomatic Grade 2 hypertension) lasting 2 weeks or longer, and abnormal laboratory findings (except $<2\text{g}/24\text{h}$ proteinuria). After the toxicity resolves, route of subsequent apatinib administration should be adjusted accordingly.

In the course of the study and based on the above regulations for dose modification, the investigator may modify the dose appropriately by comprehensively considering the drug-related toxicity in the subjects (if a subject experiences multiple Grade 2 drug-related toxicity and shows poor tolerance to the drugs, the route of apatinib administration can be adjusted after treatment interruption and toxicity recovery).

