During the trial, if a subject has fever ($>38\text{ }^{\circ}\text{C}$) and needs to use medications for corrective treatment, or in case of obvious wheezing, polypnoea, or symptoms of suffocation, the administration of SHR-1210 is skipped for the current or next scheduled time of SHR-1210 administration before the symptoms are recovered. After the symptoms are relieved and become stable for more than 7 days, the subjects are given SHR-1210 according to the subsequent dosing schedule. The possibility of pneumonia should be eliminated by imaging examinations before drug administration if necessary.

Once hypertensive crisis, cerebral hemorrhage, Grade \geq II pulmonary hemorrhage, other Grade \geq III hemorrhage, arterial thrombosis, or Grade IV venous thrombosis occurs during the trial, leukoencephalopathy syndrome, gastrointestinal perforation, the administration of apatinib should be discontinued, the administration of SHR-1210 should be interrupted and active symptomatic treatment should be given. The resumption of SHR-1210 treatment will depend on the toxicity recovery.

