9.3. Symptomatic Treatment for Apatinib-Related Adverse Reactions

1) Hand-and-foot syndrome (HFS)

HFS is a skin toxicity with palmar-plantar dysaesthesia or acral erythema and manifests especially in areas under pressure or force. It may occur in patients with tumor during chemotherapy or molecular targeted therapy. HFSR is characterized by numbness, dysesthesia, paraesthesia, tingling, no pain or pain, skin swelling, or erythema, desquamation, chapping, scleroma-like blisters, and severe pain.

HFS grading:

Grade 1: numbness/dysesthesia/paraesthesia, painless swelling or erythema of the hands and/or feet and/or discomforts that does not affect normal activities.

Grade 2: painful erythema and swelling of the hands and/or feet and/or discomforts affecting patients' activities of daily living.

Grade 3: wet desquamation, ulcers, blisters, or severe pain of hands and/or feet and/or severe discomforts that causes the patients to be unable to work or perform activities of daily living. Intense pain and loss of skin function, relatively rare.

Symptomatic treatment and management of HFS:

Some necessary symptomatic and supportive treatments must be taken, including: strengthen skin care, keep skin clean, and avoid secondary infections; avoid pressure or friction; use moisturizers or lubricants, topically use lotions or lubricants containing urea and corticosteroids; topically use antifungal or antibiotic treatment if necessary.

Note: If a HFS of Grade 3 or above occurs for more than 3 consecutive times with an aggravating trend, the subject should discontinue the study treatment and withdraw from the clinical study.

2) Hypertension

Patients should be strictly screened according to blood pressure requirements in the inclusion and exclusion criteria prior to enrollment. Patients with hypertension can control the blood pressure by adjusting the dose of or adding new antihypertensive drugs before administering the investigational drug. The blood pressure must be under 140/90 mmHg (average of 2 blood pressure measurements taken at least 24 h apart) before randomization.

Monitoring and handling of such hypertension: Blood pressure should be monitored at least 3 times a week during the first 2 cycles of the targeted pharmacological treatment.

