Note: Patients with cerebral hemorrhage, Grade II or higher pulmonary hemorrhage, and Grade III or higher hemorrhage should stop the study treatment immediately, undergo symptomatic treatment, terminate apatinib administration, and discontinue SHR-1210 administration. Consider whether to resume SHR-1210 as appropriate after symptoms resolve or disappear.

4) Proteinuria

All subjects should be closely monitored for proteinuria throughout the entire treatment period, especially for those with a history of hypertension. For those with a urine protein result of ++ to +++ in 2 consecutive tests, a 24-h urine protein assay is required. For those with urine protein of ++++ and above, a 24-h urine protein assay is required.

Note: In case of nephrotic syndrome, the subject should discontinue the treatment permanently and withdraw from this clinical study.

5) Thrombosis

If any arterial thrombosis (such as cerebral ischemia, stroke, angina pectoris, myocardial infarction, etc.) occurs, the subject should discontinue the treatment immediately and withdraw from the study. In case of any symptomatic IV venous thrombosis, the subject should discontinue the treatment and withdraw from the study.

Once the symptoms are observed, symptomatic treatment, surgery, or anticoagulants shall be immediately given.

6) Fatigue and weakness

Fatigue and weakness are common tumor-related clinical symptoms, the cause of which might be electrolyte disturbance, abnormal liver function, abnormal cardiac function, etc. Also, fatigue and weakness are common adverse reactions of targeted anti-angiogenic drugs, such as sunitinib, pazopanib, and sorafenib. Clinical reports show that targeted anti-angiogenic drugs may increase the incidence of fatigue and weakness through hypothyroidism.

In previously completed clinical trial of apatinib, subjects in the test group showed a higher incidence of fatigue and weakness than those in the control group, and the mechanism behind the increased incidence of fatigue and weakness caused by apatinib is yet unidentified.

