Therefore, close attention should be paid when a patient shows and reports Grade II or higher fatigue and weakness. In the case of Grade III or higher fatigue and weakness, the patient should be admitted to the hospital immediately for detailed examinations to exclude possible reasons such as electrolyte disturbance, abnormal liver function, cardiac dysfunction (ECG, echocardiography), and abnormal hormone levels (adrenal hormones, thyroid hormones). A symptomatic treatment should be given and the dose should be interrupted or modified according to the principle of dose modification.

7) Abdominal pain

Abdominal pain is not uncommon in the treatment with apatinib, which are mostly a concomitant symptom of tumor. Also, gastrointestinal perforation occasionally occurs in clinical trials of apatinib and other anti-angiogenic drugs. For subjects with abdominal pain, the investigator should be cautious of potential gastrointestinal perforation. Upon the observation of gastrointestinal perforation, the drug should be discontinued immediately, and the subject should withdraw from the trial and be given an active symptomatic treatment.

8) Interstitial pulmonary fibrosis

The clinical physicians should fully understand the conditions of subjects and be familiar with the drugs that may lead to pulmonary toxicity. The clinical symptoms and changes in chest X-ray or CT are closely monitored. Once cough, chest tightness, labored breathing, dyspnea, and hemoptysis of unknown causes, the drug should be discontinued as soon as other causes (such as infection and heart failure) are ruled out. Alveolar lavage fluid analysis and surgical lung biopsy are important means to diagnose interstitial lung disease. Currently, no therapy yields a satisfactory result against pulmonary fibrosis, and correction of hypoxemia and timely administration of corticosteroids are recommended following "Guidelines for Diagnosis and Treatment of Idiopathic Pulmonary (Interstitial) Fibrosis" issued by the Chinese Medical Association Respiratory Diseases Branch.

Note: Consult specialists when necessary.

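### Protocol 5.3 and 9.3 contradict each other on SHR-1210 after arterial thrombosis, Grade IV venous thrombosis or gastrointestinal perforation, so exposure, discontinuation counts and TTF depend on which section a site follows

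*Protocol*

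**What the plan says.** **Protocol 9.3.** The notes on individual toxicities give these instructions:

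- Arterial thrombosis: "the subject should discontinue the treatment immediately and withdraw from the study".
- Venous thrombosis: "In case of any symptomatic IV venous thrombosis, the subject should discontinue the treatment and withdraw from the study".
- Gastrointestinal perforation: "the drug should be discontinued immediately, and the subject should withdraw from the trial".
- Hand-and-foot syndrome of Grade 3 or above, occurring more than three consecutive times with a worsening trend: "the subject should discontinue the study treatment and withdraw from the clinical study".
- Nephrotic syndrome: permanent discontinuation and withdrawal.

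**Protocol 5.3.** The closing paragraph groups arterial thrombosis, Grade IV venous thrombosis and gastrointestinal perforation with the serious hemorrhages and other events. For all of them "the administration of apatinib should be discontinued, the administration of SHR-1210 should be interrupted and active symptomatic treatment should be given", and resumption of SHR-1210 is left to depend on recovery. For hand-and-foot syndrome, Table 1 does not suspend SHR-1210 at Grade 3, and its stopping rule is "Discontinue apatinib treatment if Grade 3 hand-and-foot syndrome recurs after 2 modifications". The general text adds: "Subjects may continue SHR-1210 as monotherapy if apatinib treatment is discontinued". Neither 5.3 nor Table 1 names nephrotic syndrome.

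**Follow-up after withdrawal.** Protocol 4.3.2 states: "Patients showing no progressive disease need to be continuously followed-up for imaging evaluation", until progression or a new anti-tumor treatment. It also continues survival follow-up unless consent to further information or contact is withdrawn. Sections 3.1, 6.3 and 6.4 agree.

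**The concern.** A site managing one of these events finds two instructions for SHR-1210 in one protocol. Under 5.3 the drug is on hold and may come back. Under 9.3 the subject has left the study and it cannot. Nothing says which section prevails.

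This is first an inconsistency in a safety rule, which is reason enough to correct it. It also affects the analysis. The SAP summarises exposure duration and relative dose intensity for each drug (5.5.1 and Table 1), tabulates events that stop SHR-1210, apatinib or both (5.5.2), and defines TTF by treatment termination or death (4.1.2.9). For affected subjects, each of these would reflect the section the site happened to read as well as the toxicity. In addition, 9.3 does not say what withdrawal means for data collection and does not refer to 4.3.2.

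**Working it through.** The plan gives no figure on this point, so the first check sets the text side by side.

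| Event | Protocol 5.3 / Table 1 | Protocol 9.3 | Finding |
|---|---|---|---|
| Arterial thrombosis | Apatinib stopped; SHR-1210 interrupted, may resume | Treatment stopped; withdrawn | Direct contradiction |
| Grade IV venous thrombosis (9.3: symptomatic IV) | As above | As above | Direct contradiction, reading IV as Grade IV; 9.3 adds symptomatic |
| Gastrointestinal perforation | As above | Drug stopped; withdrawn | Direct contradiction |
| Hand-and-foot syndrome | Apatinib stopped if Grade 3 recurs after 2 modifications; SHR-1210 alone permitted | Treatment stopped and withdrawn after more than 3 consecutive occurrences, worsening | Actions conflict; triggers differ |
| Nephrotic syndrome | Not named; nearest row is Grade 3 proteinuria without significant creatinine increase | Permanent stop; withdrawn | No opposing rule |

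This is not just how 9.3 is phrased. Its hemorrhage note ends apatinib and lets SHR-1210 be reconsidered after recovery, in line with 5.3. So 5.3 puts hemorrhage, thrombosis and perforation under one instruction, and 9.3 separates them.

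**Hand-and-foot triggers.** Suppose each Grade 3 onset leads to one modification. Table 1 then changes the apatinib schedule at onsets one and two and stops apatinib at onset three. The 9.3 trigger needs at least a fourth consecutive occurrence, plus a worsening trend. By then Table 1 has already stopped apatinib, and what 9.3 adds is the end of SHR-1210.

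**Exposure illustration (SAP Table 1 formulas).** Assumptions: 200 mg every 2 weeks; event after 6 doses; under 5.3, the full 12-week interruption that section allows, then 6 more doses. Duration is last dose minus first dose plus 14 days.

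- Under 9.3: 5 × 14 + 14 = 84 days, or 3 four-week cycles. Dose 6 × 200 = 1200 mg. Intensity 1200 / 3 = 400 mg per cycle, against 400 planned: 100%.
- Under 5.3: 84 + 84 + 84 = 252 days, or 9 cycles. Dose 12 × 200 = 2400 mg. Intensity 2400 / 9 = 266.7 mg per cycle: 66.7%.
- TTF: an event at withdrawal under 9.3. Under 5.3 it is still running while SHR-1210 continues, if treatment termination means the end of both drugs, which the SAP does not say.

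**Imaging interval.** On treatment, scans fall every 2 cycles (8 weeks) for 12 cycles, then every 3 cycles (12 weeks). After treatment ends for reasons other than progression they fall every 3 months: 3 × 30.4375 / 7 = 13.0 weeks. Protocol 7.1.2 also says that discontinuation or delay does not affect tumor assessments, which sits awkwardly with the 3-month schedule.

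**Bound on the ORR effect.** The 10% rule applies to the sorafenib-refractory cohort (Protocol 11.2), planned at 80 and expandable to 120. Clopper-Pearson lower limits:

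- n = 80: 14 responders give 9.9%, 15 give 10.9%; 15 are needed.
- n = 120: 19 give 9.8%, 20 give 10.5%; 20 are needed.

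At the planned 25% ORR, expected responders are 20 and 30. Assume that 1% to 5% of subjects have such an event, and that 10% to 25% of the responders among them are unconfirmed at that time and never confirmed. The documents give neither rate. Expected responders lost:

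- n = 80: from 80 × 0.01 × 0.25 × 0.10 = 0.02 to 80 × 0.05 × 0.25 × 0.25 = 0.25.
- n = 120: from 120 × 0.01 × 0.25 × 0.10 = 0.03 to 120 × 0.05 × 0.25 × 0.25 = 0.38.

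One lost responder reverses the conclusion only if the count would otherwise sit exactly on the threshold. At a true ORR of 25% that probability is 4.7% (15 of 80) or 0.9% (20 of 120).

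**The case against.** The strongest reply is that follow-up is already protected. Section 4.3.2 governs withdrawal as well as discontinuation and continues imaging and survival contact. Section 6.3 requires a scan at the end of treatment if none was done in the previous 4 weeks, then 3-monthly evaluation, and 6.4 continues survival follow-up. Section 4.3.1 uses withdrawing from and terminating treatment almost interchangeably, so withdrawal in 9.3 may mean no more than stopping treatment. This stands. A reader might infer that the subjects most harmed by treatment are lost, with PFS, DOR and OS informatively censored. The documents do not support that unless sites disregard 4.3.2, 6.3 and 6.4.

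A reader might also infer that a responder awaiting confirmation becomes a non-responder on withdrawal. That does not follow. The best-response window closes at progression or new anti-tumor treatment (Protocol 7.1.1, SAP 4.1.1), not at the end of study treatment, so a later scan can still confirm the response. The route that remains is narrow: a first response, no end-of-treatment scan because one was recent, and new therapy before a confirming scan.

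For hand-and-foot syndrome, 9.3 can be read as a later escalation step, and 5.3 only permits SHR-1210 monotherapy. That is why this conflict ranks below the other three.

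The reply does not remove the contradiction for thrombosis and perforation. Even if withdrawal means only stopping treatment, 9.3 closes the SHR-1210 option that 5.3 leaves open.

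**Conclusion.** The point holds for three events: arterial thrombosis, Grade IV venous thrombosis and gastrointestinal perforation. It holds in a weaker form for hand-and-foot syndrome.

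It should not be widened to nephrotic syndrome, for which only 9.3 has a rule. Nor should 5.3 be described as stopping apatinib alone for thrombosis and perforation, since it also interrupts SHR-1210.

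The consequence lies in SHR-1210 exposure, relative dose intensity, one-drug and two-drug discontinuation counts, TTF and scan spacing. It can be large for an individual subject, but few subjects are likely to be involved; the documents give no event rate. Under the stated assumptions the expected loss to the primary ORR count is at most about 0.4 of a responder, so the primary conclusion is not materially threatened. Correction is warranted because safety instructions should not differ by section. Which clinical rule is right is not a question for this review.

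**What to change.** 1. Reconcile the last paragraph of Protocol 5.3, the hand-and-foot row of Table 1 and the 5.3 monotherapy sentence with the 9.3 notes on hand-and-foot syndrome, thrombosis and perforation, so that each event carries one trigger and one instruction per drug. The sponsor's medical team decides the content. Making 9.3 simply defer to 5.3 would choose the clinical rule by default and, if applied to every 9.3 note, would send nephrotic syndrome to a section that does not cover it.
2. Separately, state in each 9.3 note that uses withdrawal wording, including nephrotic syndrome, that withdrawal does not end tumor-assessment or survival follow-up, which continue under 4.3.2, 6.3 and 6.4 unless consent is withdrawn.

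The cost is a protocol wording change or clarification letter. The follow-up visits are already planned, and sample size and primary analysis are unaffected.

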10. INDEPENDENT IMAGING EVALUATION

On-site imaging review will be performed at each study site, and the Independent Review Committee (IRC) will perform central review on the primary efficacy endpoint of ORR.

Imaging assessments will be performed by an experienced and qualified study physician designated by each study site. All the imaging data related to efficacy assessment should be archived on CD and sent by each study site to the Independent Review Committee for evaluation at regular intervals.

Independent imaging assessment will be performed blindly by two independent radiologists. In the event of disagreement between these 2 independent radiologists, a third radiologist will make the final judgment. See the "Independent Review Committee Charter" for details.

Treatment response will be evaluated by independent radiologists in accordance with the RECIST 1.1 and mRECIST criteria.

11. DATA ANALYSIS/STATISTICS

Data analysis will not be performed by study sites (data from all participating sites will be combined).

Screen failure subjects (those who signed the informed consent form but did not receive any treatment) and the reasons for screen failures will be included in the statistical analysis.

In addition, these subjects will be reported in a separate list.

